6 STUDY PROCEDURES

6.1 Schedule of Events

Activity	Phone Screen	Visit 1 Screen Visit		Visit 2 Baseline Visit	Visit 3	Visit 4	Visit 5	Phone Check 1	Visit 6/ET	Phone Check 2	Phone Check 3
		Day \geq -45		Week 1	Week 4	Week 12	Week 26	Week 39	Week 52	Week 78	Week 104
		SVa	SVb	Day 1	Day 28 + 14	Day 84 \pm 5	Day 182 \pm 14	Day 273 \pm 5	Day 364 \pm 28	Day 546 \pm 28	Day 728 \pm 28
Informed Consent		X									
Inclusion/Exclusion Review	X	X		X							
Demographics	X	X									
Medical History Review	X	X	X	X	X	X	X	X	X	X	X
Concomitant Medication Review	X	X	X	X	X	X	X	X	X	X	X
Family History Review		X									
Vital Signs, Height, and Weight ¹		X	X	X	X	X	X		X		
Physical & Neurological Exam ²		X									
Fundoscopy						X			X		
Screening Labs ³		X									
BCG Vaccination				X	X						
Injection Site Monitoring ⁴					X	X	X		X		
LP Safety Labs ⁵		X				X			X		
Blood Draw for Biomarkers			X	X	X	X	X		X		
CSF Draw for Eligibility & Biomarkers			X			X			X		
Optional MRI ⁶				X					X		
RBANS, NPI-Q, HADS				X		X	X		X		
MoCA, FAQ		X				X	X		X		
CDR				X					X		
DCT Clock				X			X		X		
Adverse Event Review		X	X	X	X	X	X	X	X	X	X

[1] Height measured at screening only. Weight measured at screening, week 26, and week 52

[2] Physical and neurological examinations will be performed at screening and at any other time if indicated per clinician investigator judgement

[3] Eligibility lab tests include CBC w/ diff, CMP, TSH, Folate, B12, HIV antibodies, serum immunoglobulins, ESR, CRP, QuantiFERON-TB Gold Test/T-spot TB test, urinalysis, PT/INR

[4] Vaccination site monitoring may include photographs of the injection site if indicated per clinician investigator judgement

[5] LP safety labs include PT/INR and CBC w/ diff

[6] Multi-sequence MRI for structural and functional measures include T1 MP-RAGE, T2 FLAIR, DWI, DTI, BOLD, ASL

An Open Label Trial to Evaluate the Effects of BCG Immunization on Biomarkers of Inflammation/Immune Response and Alzheimer's Disease in Adults with Mild Cognitive Impairment and Mild-to-Moderate Dementia due to Alzheimer's Disease

Version Date#: October 13, 2022/Version 3.3

6.1.1 RCT roll over participant schedule

Participants enrolled in the original randomized-controlled BCG trial will be invited to roll into the open-label trial at their scheduled Visit 3 using a Consent addendum. After unblinding the randomization schedule, participants will be told which study vaccine they received at their Baseline Visit.

If at Baseline, the participant received BCG, they will proceed in the study along the same schedule outlined in the Schedule of Events, receiving their second BCG vaccine at Visit 3/Day 28.

If at Baseline, the participant received placebo, their Day 28 visit will become their new Day 1 visit. At this Day 1 visit we will collect vitals and administer the first BCG vaccine. No additional blood or CSF will be collected, nor will any cognitive testing be performed. The participant will receive their second BCG vaccine approximately 1 month after the first BCG vaccine, and continue on the Schedule of Events outlined after the Day 1 visit in Section 6.1. The total time in the study will be extended by 1 month for participants originally assigned to the placebo arm of the randomized controlled trial.

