6.2.2 Baseline Visit/Visit 2 (Day 1)

All subjects who pass screening will return to MGH CNY for the Baseline visit. At this visit, baseline clinical measures will be collected, and the first BCG injection will be administered. The Baseline visit will occur within 45 days of the screening visit. Baseline measures may be collected up to 3 days before the first BCG dose is administered. The date of the first BCG injection will be considered “Day 1”. The visit will take approximately 3-4 hours and will include:

- Vital signs
- Review inclusion and exclusion criteria
- Assess for changes to medical history, concomitant medications and/or adverse events
- Neurocognitive and behavioral assessments: RBANS (form a), NPI-Q, HADS, DCT Clock
- Blood draw for biomarkers
- MRI (optional)
- First BCG administration followed by 30 minutes of monitoring

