6.2.3 Visit 3 (Day 28 + 14 days)

Subjects will be asked to return to MGH CNY for a second BCG injection visit 28 (+14) days after the first vaccination. This visit will take approximately one hour and will include:

- Vital signs
- Assess any changes to medical history, concomitant medications and/or adverse events
- Blood draw for biomarkers
- Injection site monitoring
- Second BCG dose administered followed by 30 minutes of monitoring

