6.3.3 Phlebotomy for Research: Target Engagement, Cytokine Levels and Biomarker Analysis

Subjects will provide additional blood samples for biomarker analysis at all in person visits. Target engagement will determine whether the subject's immune system has responded to BCG. In general, whole blood will be either collected and utilized for biochemical / metabolic assays, or spun in EDTA-containing tubes with plasma being frozen for cytokine analysis of IIR and / or AD biomarkers. Remaining plasma may be used for other biochemical analyses. Peripheral blood mononuclear cells (PBMCs) will be isolated from the cell pellets, some of which will be frozen for later culturing and cell-stimulation studies. Other PBMCs will be further isolated into subpopulations of cells and frozen for epigenetic analyses (e.g. ATACseq) and possibly subject to other immunostaining or quantitative biochemical assays.

In addition to these analyses, blood will also be collected for routine blood tests that will be used for research purposes including Complete Blood Count with differential (CBC w/ diff), C-Reactive Protein (CRP), and Erythrocyte Sedimentation Rate (ESR). CRP and ESR tests will be performed at a central laboratory. CBC w/ diff may be performed either on-site using a CLIA-waived point-of-care device (Sysmex XW-100 CBC Analyzer) or at a central laboratory. Blood volumes collected at each visit are detailed in Table 2.

Table 2. Blood Collection for Research

Visit	Blood volume required for biomarker analyses (mL)	Volume required for routine tests(mL)	TOTAL (mL)
Screening (SV1a)	0	0	0
Screening (SV1b)	75	0	75
Week 1	50	0	50
Week 4	75	3 for CBC w/ diff	78
Week 12	125	9 for CBC w/ diff, ESR, CRP	134
Week 26	125	9 for CBC w/ diff, ESR, CRP	134
Week 52	125	6 for ESR, CRP	131
Total	575	27	602

Blood processing will occur on site at MGH. Blood samples will be de-identified, codified, and stored on-site. Blood samples will be stored for research until they are used, damaged, or otherwise unfit for analysis. Some biomarker analyses may be done at Harvard-affiliated core labs.

Samples drawn for biomarker research may also be used for genome analyses in the future. Subjects will not receive the results of these studies if they are done and genetic research results will not be placed in the subjects' medical records.

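### Placebo roll-overs enter with CSF and cognitive baselines about 28 days older than those of direct enrollees, and section 8.3 counts that untreated interval as post-BCG change

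*Combined protocol and SAP*

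**What the plan says.** Section 6.1.1 covers participants who move over from the randomized trial at their Visit 3. Those who had BCG keep their original Day 1 and are not affected. For the others: "If at Baseline, the participant received placebo, their Day 28 visit will become their new Day 1 visit". At that visit the section provides for vital signs and the first BCG injection, and adds: "No additional blood or CSF will be collected, nor will any cognitive testing be performed". Later visits follow the ordinary schedule, counted from the new Day 1.

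For direct enrollees, section 6.2.2 keeps baseline close to dosing: "Baseline measures may be collected up to 3 days before the first BCG dose is administered". RBANS, NPI-Q, HADS and DCT Clock have their baseline at Visit 2, as does the optional MRI. CSF, MoCA and FAQ have theirs at screening, which may precede Visit 2 by up to 45 days.

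Section 8.3 analyses change from the screening or baseline value to each later visit. Biofluid and clinical endpoints use a repeated-measures mixed model with the baseline value as covariate, and MRI uses observed cases. The section does not say which value is baseline for a placebo roll-over, makes no adjustment for elapsed time and plans no sensitivity analysis.

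On blood the text is not settled. Section 6.1.1 rules out additional blood at the new Day 1. The Schedule of Events and section 6.2.3 put a biomarker draw at Visit 3 ("Blood draw for biomarkers"), and section 6.3.3 says: "Subjects will provide additional blood samples for biomarker analysis at all in person visits".

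**The concern.** The study has no control arm, so any biomarker, cognitive or imaging effect of BCG is read from change since baseline. That reading needs the baseline to sit just before the first BCG dose, or at least at a similar distance from it in everyone. For placebo roll-overs it does not. Their change at a given visit label covers a longer period than the label says, and the first part of that period is before any BCG. The model in section 8.3 would pool this with the change in direct enrollees and attribute all of it to the time after vaccination. This results from following the stated rules, not from a detail left open.

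**Working it through.** The plan states no figure for the lag or its effect, so there is nothing to reproduce. The check is visit-day arithmetic.

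**Inputs**
- Lag L from the Visit 2 baseline to first BCG in a placebo roll-over: 28 days nominal, because the Day 28 visit becomes Day 1 (section 6.1.1). This agrees with the stated one-month extension of study time.
- Upper values of L: 42 days with the +14-day Visit 3 window (section 6.2.3), and 45 days with the 3-day allowance added (section 6.2.2). Both assume that the randomized trial used this protocol's windows; its schedule is not in the documents.
- Direct enrollees: L = 0 to 3 days.
- Visit day V, counted from the first injection: 84, 182 and 364.

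**Formula.** Interval = L + V; untreated share = L/(L + V).

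| Visit | Direct, at most | L = 28 | L = 42 | L = 45 |
|---|---|---|---|---|
| Week 12 | 3/87 = 3.4% | 28/112 = 25.0% | 42/126 = 33.3% | 45/129 = 34.9% |
| Week 26 | 3/185 = 1.6% | 28/210 = 13.3% | 42/224 = 18.8% | 45/227 = 19.8% |
| Week 52 | 3/367 = 0.8% | 28/392 = 7.1% | 42/406 = 10.3% | 45/409 = 11.0% |

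The Week 12 row applies to RBANS, NPI-Q and HADS; DCT Clock is not done then. It joins at Weeks 26 and 52. Any MRI is affected at Week 52 only.

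**Screening measures (CSF, MoCA, FAQ).** The baseline is 0 to 45 days old at first BCG in direct enrollees. In placebo roll-overs it is 28 to 42 + 45 = 87 days old, on the same assumption. The excess is again 28 days, or up to 42.

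**Blood.** If the Visit 3 draw is taken before BCG and used as baseline, the lag is about 0. If no blood is drawn, the lag is as above, and at Week 4 (V = 28) the untreated share is 28/56 = 50%, or 42/70 = 60%.

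**Pooled effect.** The number of placebo roll-overs is not given. As an illustration, assume k of the approximately 15 subjects in section 8.1 and L = 28. The mean Week 12 interval then rises by 28k/15 days, a proportion 28k/(15 × 84):
- k = 0: none
- k = 1: 2.2%
- k = 3: 6.7%
- k = 5: 11.1%
- k = 8: 17.8%

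The documents give no rate of change or standard deviation for any endpoint, so these times cannot be turned into bias in outcome units.

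**The case against.** The best defence is that the omission is deliberate. Repeating the baseline would mean another lumbar puncture and another cognitive session about a month after the last, and section 6.1.1 openly declines both. Direct enrollees already have CSF, MoCA and FAQ baselines up to 45 days old. In a single-arm study the whole year of follow-up mixes natural progression with any BCG effect for everyone, and 28 days adds only 28/364 = 7.7% to the Week 52 interval. All of that stands, and it is why the point is minor. It does not explain why the analysis section ignores a difference that the design section creates, when allowing for it is nearly free.

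Three stronger readings are tempting, and the documents do not support them.

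- *A quarter of the Week 12 change is artefact.* The 25% is a share of time. Nothing in the documents says how much any measure moves in 28 days.
- *Post-BCG visits are out of window.* They are not. Day 1 restarts at first BCG, so only the age of the baseline is affected.
- *Placebo-period events will enter the primary safety endpoint.* Section 8.2 starts counting at the first dosing at Baseline. Section 6.1.1 does use that word for the placebo visit ("participants will be told which study vaccine they received at their Baseline Visit") and counts the placebo month as study time ("The total time in the study will be extended by 1 month for participants originally assigned to the placebo arm"). But section 6.2.2 fixes Day 1 by the BCG dose ("The date of the first BCG injection will be considered" Day 1), and section 6.1.1 moves Day 1 to that dose. The inclusion of diluent among the study drugs in section 7.1 does not help this reading. Table 3 and section 7.4 show it as the fluid for reconstituting BCG, and no section says that the trial's placebo was that diluent. What is left is a wording ambiguity, mostly resolved towards first BCG.

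**Conclusion.** The point holds, as minor. As written, the plan gives placebo roll-overs CSF, cognitive and any MRI baselines about 28 days older relative to first BCG than those of direct enrollees, and section 8.3 treats that interval as post-BCG time. The 28-day figure rests on section 6.1.1 alone; the 42- and 45-day figures need the randomized trial to have used the same windows. Whether blood is affected depends on an unresolved conflict between section 6.1.1 and the Schedule of Events, section 6.2.3 and section 6.3.3. The effect on pooled results cannot be calculated without the number of placebo roll-overs and may be nil. The text is clear on the mismatch; a material effect on the conclusions is not shown.

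**What to change.** 1. **Section 8.3.** Repeat the biomarker, cognitive and MRI change analyses without placebo roll-overs, or adjust for the actual time from baseline sample to first BCG. Use any Visit 3 blood drawn before BCG as their blood baseline. Naming the last pre-BCG value as baseline is not enough for CSF and cognition, because that value is the old one; there, only exclusion or adjustment helps. For Visit 2 measures the lag is close to two-valued (about 0 or about 28 days), so adjustment would be imprecise in a study of about 15, and exclusion is the simpler choice.
2. **Section 8.2.** State that treatment-emergent adverse events are counted from the first BCG dose, and list placebo-interval events separately by onset date, which sections 11.3.3 and 11.3.5 already record. This closes an ambiguity and does not correct a demonstrated error.
3. **Section 6.1.1.** Reconcile it with the Schedule of Events, section 6.2.3 and section 6.3.3 on biomarker blood at the new Day 1. If none is planned, taking the Schedule's own Day 1 sample (50 mL in Table 2) from those not yet given BCG is an optional improvement.

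The cost is a few sentences, some extra analysis of data already collected, and a smaller sample in the sensitivity analysis. The optional sample is one draw at a visit that takes place anyway. All of this should be fixed before the data are analysed, so that the baseline and the start of event counting are not chosen after seeing results.

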6.2 Study Visits

6.2.1 Screening

6.2.1.1 Telephone Pre-Screening

Subjects will be screened over the phone by study staff to determine eligibility and to ensure that the subject is safe to undergo all study assessments. These procedures include:

- Obtain verbal pre-screening informed consent from subject
- Assess inclusion and exclusion criteria
- Collect brief demographics
- Obtain neurocognitive disease diagnosis history and medical history, including COVID-19 diagnosis and previous exposure risk
- Review and document concomitant medications and therapies

During this call, study procedures will be discussed in detail and the subject will be given an opportunity to ask questions about the study. All other study procedures will take place after signing an IRB-approved consent form in-person. For those that have impaired decision making, the phone screening process will be coordinated with the study partner and will be conducted in the presence of both the study partner and the potential participant.

6.2.1.2 Screening Visits (Visit 1; Day ≥-45)

All subjects who are eligible after a telephone pre-screening will be invited to MGH CNY for Screening that will include 2 separate visits.

The first visit (SVa) will take approximately 2 hours and following procedures will be performed:

- Obtain written informed consent from subject
- Review inclusion and exclusion criteria
- Obtain medical and family history including COVID-19 history, concomitant medications and therapies
- Vital signs, height, and weight
- Obtain demographic information
- Neurocognitive and behavioral assessments: MoCA (version 8.1), CDR, FAQ
- Perform a physical, including inspection for BCG scar on either deltoid
- Perform a neurological examination
- Blood draw for screening labs

- CBC with differential
- Comprehensive metabolic panel (CMP)
- Thyroid stimulating hormone (TSH)
- B12
- Folate
- HIV antibodies
- Tuberculosis (QuantiFERON-TB Gold Test/T-Spot TB Test)
- C-Reactive Protein (CRP)
- Erythrocyte sedimentation rate (ESR)
- Serum immunoglobins (IgA, IgG, IgM)
- PT/INR
- Urinalysis
- Assess and document adverse events (AEs) after subject signs ICF

If the participant is still eligible after the first Screening visit (SVa), they will be invited to come back for a second Screening visit (SVb) which will take approximately 1 hour. The following procedures will be performed:

- Vital signs
- Blood draw for biomarkers
- Fasting CSF draw for screening (if required) and baseline biomarkers
- Assess for changes to medical history, concomitant medications and/or adverse events

6.2.1.3 Screen Failures

Any subject who signs consent will be considered enrolled in the study. If a subject fails screening, *at a minimum*, the following information should be captured and entered into the Electronic Data System (EDC).

- Inclusion/Exclusion Criteria
- Demographics
- Reason for screen failure

6.2.1.4 Re-screening

One re-screen is allowed ≥ 30 days after the initial screening. All screening procedures will be repeated at the re-screen visit.

6.2.2 Baseline Visit/Visit 2 (Day 1)

All subjects who pass screening will return to MGH CNY for the Baseline visit. At this visit, baseline clinical measures will be collected, and the first BCG injection will be administered. The Baseline visit will occur within 45 days of the screening visit. Baseline measures may be collected up to 3 days before the first BCG dose is administered. The date of the first BCG injection will be considered “Day 1”. The visit will take approximately 3-4 hours and will include:

- Vital signs
- Review inclusion and exclusion criteria
- Assess for changes to medical history, concomitant medications and/or adverse events
- Neurocognitive and behavioral assessments: RBANS (form a), NPI-Q, HADS, DCT Clock
- Blood draw for biomarkers
- MRI (optional)
- First BCG administration followed by 30 minutes of monitoring

6.2.3 Visit 3 (Day 28 + 14 days)

Subjects will be asked to return to MGH CNY for a second BCG injection visit 28 (+14) days after the first vaccination. This visit will take approximately one hour and will include:

- Vital signs
- Assess any changes to medical history, concomitant medications and/or adverse events
- Blood draw for biomarkers
- Injection site monitoring
- Second BCG dose administered followed by 30 minutes of monitoring

6.2.4 Visit 4 (Day 84 ± 5 days)

Subjects will be asked to return to MGH CNY 84 (\pm 5) days after the first injection. This visit will take approximately three hours and will include:

- Vital signs
- Assess any changes to medical history, concomitant medications and/or adverse events
- Blood draw for safety
- Blood draw for biomarkers
- Focused Exam: Fundoscopy
- Neurocognitive and behavioral assessments: RBANS (form b), NPI-Q, HADS, MoCA (version 8.2), FAQ
- Blood draw for LP safety labs
- Blood draw for biomarkers
- Fasting CSF draw for biomarkers
- Injection site monitoring

6.2.5 Visit 5 (Day 182 ± 14 days)

Subjects will be asked to return to MGH CNY 182 (\pm 14) days after the first injection. This visit will take approximately two hours and will include:

- Vital signs
- Assess any changes to medical history, concomitant medications and/or adverse events
- Blood draw for biomarkers
- Neurocognitive and behavioral assessments: MoCA (version 8.3), FAQ, RBANS (form c), NPI-Q, HADS, DCT Clock
- Injection site monitoring

6.2.6 Phone Check 1 (Day 273 ± 5 days)

Subjects will be asked to complete a check-in phone call 273 (\pm 5) days after the first injection. This will take approximately fifteen minutes and will include:

- Assess any changes to medical history, concomitant medications and/or adverse events

6.2.7 Visit 6 (Day 364 ± 28 days)

Subjects will be asked to return to MGH CNY for the final in-person visit at Day 364 (\pm 14 days) to assess study outcomes. This visit will take approximately four hours and will include:

- Vital signs
- Assess any changes to medical history, concomitant medications and/or adverse events
- Neurocognitive and behavioral assessments: FAQ, MoCA (version 8.1), CDR, RBANS (form a), NPI-Q, HADS, DCT Clock
- Blood draw for biomarkers
- Blood draw for LP safety
- Focused Exam: Fundoscopy
- Fasting CSF draw for biomarkers
- MRI (optional)
- Injection site monitoring

6.2.8 Phone Check 2 & 3 (Day 546 ± 28 days, Day 728 ± 28 days)

Subjects will be asked to complete a check-in phone call approximately 18 months and 2 years after the first injection to monitor safety. This will take about fifteen minutes and will:

- Collect any changes to medical history, concomitant medications, and/or adverse events

If the subject reports any new adverse events at the Phone Check that may require follow up, they will be referred to their primary care provider for further evaluation.

6.2.9 Early Termination Visit

If the subject withdraws from the study before completion of all study visits, they may be invited to return to MGH CNY for a final visit. This visit will take approximately four hours and will include the following measures:

- Vital signs
- Assess any changes to medical history, concomitant medications and/or adverse events
- Neurocognitive and behavioral assessments: FAQ, MoCA (version 8.1), CDR, RBANS (form a), NPI-Q, HADS, DCT Clock
- Blood draw for biomarkers
- Blood draw for LP safety

- Fasting CSF draw for biomarkers
- MRI (optional)
- Injection site monitoring

The option to decline any of the early termination procedures or the entire visit will be given to all participants withdrawing from the study.

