5.4 Early Termination Visit (ET)

Subjects who decide to withdraw from the study at any point after receiving the initial BCG injection may be invited to come in for an Early Termination Visit.

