6.4 Neurocognitive Assessments

6.4.1 Montreal Cognitive Assessment (MoCA)

The Montreal Cognitive Assessment (MoCA) is a commonly utilized questionnaire in clinical trials and research settings to measure levels of cognitive impairment.⁵⁰ The MoCA measures five areas of cognitive function: orientation, visuospatial, attention and calculation, recall, and language. The MoCA (version 8.1) will take approximately 15 minutes to complete. The MoCA will be administered at the Screening visit (version 8.1) to determine subject eligibility (MoCA ≥ 8) and repeated at Week 12 (version 8.2), Week 26 (version 8.3), and Week 52 (version 8.1).

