6.4.2 Repeatable Battery for the Assessment of Neuropsychological Status Update (RBANS)

The RBANS⁵¹ is a commonly used 25-minute, standardized neurocognitive battery. The RBANS measures five neurocognitive domains, with twelve subtests measuring cognitive decline or improvement with immediate memory (List Learning and Story Memory), visuospatial/constructional (Figure Copy and Line Orientation), language (Picture naming and Semantic Fluency), attention (Digit Span and Coding), and delayed memory (List Recall, List Recognition, Story Memory, and Figure Recall). The RBANS has been shown to be effective at both detecting and characterizing forms of dementia. The Delayed Memory domain has been shown to be particularly sensitive to discriminating mild cognitive impairment (MCI) due to Alzheimer's disease from controls, and also is predictive of cerebral amyloid burden. The RBANS will be administered at Week 1 (form a), Week 12 (form b), Week 26 (form c), and Week 52 (form a).

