8.3 Biofluid Biomarker, Clinical and Neuroimaging Endpoints

The change in the following assessments from Screening and/or Baseline to each post-baseline visit as described below based on the Schedule of Activities after BCG vaccination:

- Biochemical Biomarkers in Blood (Screening/Baseline, Weeks 4, 12, 26, 52) and CSF (Screening/Baseline, Weeks 12, 52) : a) Target engagement (e.g., PPD-induced PBMC cytokine release); b) Pharmacodynamic response (e.g., circulating cytokines in blood and CSF); c) AD pathophysiology (e.g., amyloid-b, tau and neurofilament light in CSF and blood); d) PBMC stimulation with AD-relevant immunogens (e.g., amyloid-b); e) Other novel biochemical biomarkers
- Clinical Neurocognitive and Behavioral Measures (Baseline, Week 12, 26 and 52): MoCA, RBANS, CDR-SB, NPI-Q, HADS, DCT Clock and FAQ
- Multi-Sequence Structural and Functional MRI (Baseline, Week 52)

Mixed-effects Model for Repeated Measures models will be used for biofluid and clinical endpoints to calculate differences at each post-baseline visit in which the biomarker is collected using baseline assessment as a covariate. Observed Case analysis will be used for differences in change of MRI measures over 52 weeks.

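### Every early termination visit uses RBANS form a and MoCA 8.1, which defeats the form rotation before Week 26, and section 8.3 does not say how early termination data are analysed

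*Combined protocol and SAP*

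**What the plan says.** Sections 6.4.1 and 6.4.2 rotate the test forms. For RBANS: "The RBANS will be administered at Week 1 (form a), Week 12 (form b), Week 26 (form c), and Week 52 (form a"). For MoCA, version 8.1 is given at Screening and the test is then "repeated at Week 12 (version 8.2), Week 26 (version 8.3), and Week 52 (version 8.1"). Section 6.2.2 confirms form a on Day 1: "Neurocognitive and behavioral assessments: RBANS (form a), NPI-Q, HADS, DCT Clock".

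Section 6.2.9 repeats the Week 52 cognitive list for the ET visit, with no condition on when the withdrawal happens: "Neurocognitive and behavioral assessments: FAQ, MoCA (version 8.1), CDR, RBANS (form a), NPI-Q, HADS, DCT Clock". Section 5.4 opens that visit to withdrawals at any time after the first injection: "Subjects who decide to withdraw from the study at any point after receiving the initial BCG injection may be invited". Attendance is voluntary: "The option to decline any of the early termination procedures or the entire visit will be given to all participants withdrawing from the study".

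In the Schedule of Events (section 6.1), ET has no column of its own. It shares one with Visit 6, headed Week 52, Day 364 ± 28. Section 8.3 lists Weeks 12, 26 and 52 for the clinical measures, Weeks 12 and 52 for CSF, and Week 52 for MRI. It specifies a mixed model for repeated measures (MMRM) by visit and, for imaging, "Observed Case analysis will be used for differences in change of MRI measures over 52 weeks". It does not mention ET data.

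**The concern.** Two things looked wrong.

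The first is the choice of forms. The protocol gives no reason for the rotation, but its effect is that no form recurs for about a year. Fixing form a and 8.1 at ET undoes this for early withdrawals, although alternate forms are available and unused. A repeat on the same form after a short interval may carry a practice gain in RBANS and MoCA.

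The second is the analysis. The only Schedule slot that an ET value can occupy is headed Week 52, and section 8.3 ties its endpoints to the Schedule. An analyst could file an early cognitive, CSF, blood, CDR or MRI value under Week 52, move it to the nearest visit, or drop it, and each choice would be consistent with the text. In a single-arm, open-label trial of about 15 people, that choice should not be left until the data have been seen. It matters most for MRI and CDR-SB, because their single post-baseline slot leaves no other scheduled visit for an ET value.

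**Working it through.** The plan gives no figure of its own to reproduce here. The check is day arithmetic on the stated visit days, followed by a reading of the Schedule against section 8.3.

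**Inputs.** First BCG is Day 1. Visit 4 is Day 84 ± 5, Visit 5 is Day 182 ± 14 and Visit 6 is Day 364 ± 28 (section 6.1). The Screening gap is "The Baseline visit will occur within 45 days of the screening visit". Baseline measures may be taken up to 3 days before the first dose (section 6.2.2). The sample size is about 15 (section 8.1), with 12 expected completers (section 4.2).

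**Interval to repeat of RBANS form a.**
- As planned: 364 − 1 = 363 days. With ± 28 this is 335 to 391 days.
- ET before nominal Day 84: less than 84 − 1 = 83 days, or 86 if Baseline testing was 3 days early. That is about 12 weeks at most.
- ET between Day 84 and Day 182: 83 to 182 − 1 = 181 days, with form c still unused.

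**Interval to repeat of MoCA 8.1.**
- As planned, at nominal Day 364: 363 days, up to 363 + 45 = 408.
- ET before Day 84: less than 83 + 45 = 128 days, about 18 weeks.
- ET between Day 84 and Day 182: 83 to 181 + 45 = 226 days, with 8.3 still unused.

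For roll-over participants first given placebo, section 6.1.1 resets Day 1 at the Day 28 visit without new cognitive testing. Their intervals are about four to six weeks longer. After Week 26 all three forms of each test have been used, and form a and 8.1 come next in the rotation anyway. The form problem is therefore confined to withdrawals before Week 26, and back-to-back repetition to those before Week 12.

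**Fit to the Week 52 column.** The lower edge of its window is 364 − 28 = Day 336. An ET before Day 84 is more than 336 − 84 = 252 days too early. It shares the column's procedures but cannot meet the column's window.

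**Weight of one value, if it were labelled Week 52.** 1/15 = 6.7% of the mean with 15 values, and 1/12 = 8.3% with 12.

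**Window conflict.** The Schedule and the heading of section 6.2.7 give Visit 6 as ± 28 days. The text of 6.2.7 gives ± 14, that is Day 350 to 378 instead of Day 336 to 392.

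**The case against.** A reader might infer that the plan turns an early ET value into a Week 52 outcome, in effect carrying the last observation forward. The documents do not support that. The shared column lists which procedures are done, and its own window excludes an early ET. Section 8.3 names Weeks 12, 26 and 52 and does not name ET. Neither MMRM nor an observed-case analysis carries values forward. Section 12.3 adds that the data system can query out-of-window entries. All of this stands. What remains is that no passage says what to do with the value, and a query does not settle how it is analysed.

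A reader might also put a size on the bias. If 3 of 15 had ET values near Week 13 counted as Week 52 and decline were linear, the mean decline would be understated by 0.2 × (1 − 13/52) = 15%. That calculation assumes the number affected, the shape of decline and attendance at a visit that may be declined. Week 13 also falls after the Week 12 forms, so it does not describe the back-to-back repeat. The direction is open too: people who leave because they are worsening could pull the mean down, and practice gain concerns only RBANS and MoCA, not CDR or MRI.

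Finally, repeating the baseline form at the last visit is the plan's own approach at Week 52, and it avoids differences between forms when change is measured. That is a fair argument at a year's distance. It is weaker at a few weeks, and Weeks 12 and 26 already compare different forms with baseline.

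**Conclusion.** The point holds in two parts. First, it is established from the text that section 6.2.9 overrides the rotation of sections 6.4.1 and 6.4.2 for any ET before Week 26. Before Week 12 the repeat is of the very last forms taken. Second, the handling of ET data in section 8.3 is undefined, and the only slot in the Schedule invites a Week 52 label without requiring one.

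No bias estimate can be given, because the documents state neither a dropout rate nor a practice effect, and the visit is optional. The 7% to 8% weight of one participant is an illustration that assumes 12 to 15 values at Week 52 and that the value is labelled that way. The change is worth making because it is cheap and removes a choice that would otherwise be made after the data are known.

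**What to change.** - **Section 6.2.9:** replace the fixed forms with the next RBANS form and MoCA version in the rotation that the participant has not yet taken, reverting to form a and 8.1 once all have been used.
- **Section 6.1 and the data system:** give ET its own column and visit code.
- **Section 8.3:** assign ET data by days since first BCG. A value goes to a scheduled visit only if it falls inside that visit's window and no scheduled value exists there. It counts as Week 52 only inside the Week 52 window. All other ET values, including MRI and CDR, are listed separately.
- **Before this:** reconcile the ± 28 and ± 14 day windows for Visit 6, since the rule depends on them.

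The cost is wording in three sections, the window correction in 6.2.7 and one visit code. There are two small losses. A few early values no longer contribute to Week 52, and someone who leaves before the Visit 4 window would add no post-baseline cognitive value to the model. An early ET would also compare different forms with baseline, as Weeks 12 and 26 already do.
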